BCG vaccine:

The application of bcg vaccine as well as its storage and the materials used for application will follow the standards of the Manual of Standards and Procedures for Vaccination of the Ministry of Health (Brazil, 2014). As standardized in this Manual, the

vaccine will be applied intradermally to the lower insertion of the deltoid muscle of the right arm, except contraindications or impossibilities. Other details are described in the standard operating manual (MOP) of the study. After the intervention, participants will be under observation for 20 minutes in the study center waiting room and will be released after the period as long as they do not present adverse events.

Placebo:

A 0.1 ml of 0.9% NaCl saline solution applied intradermally in the lower insertion of the deltoid muscle of the right arm will be used as placebo, except contraindications or impossibilities. Other details are described in the standard operating manual (MOP) of the study. After the intervention, participants will be under observation for 20 minutes in the study center waiting room and will be released after the period as long as they do not present adverse events.

Blinding:

The study participants as well as the researchers, coordinators, nurses, physicians and digitizers of the study will be blind to the allocation in the experimental or control groups.

Only nursing technicians who will apply the vaccine or placebo will be aware of which group the patient will be allocated to. This professional will not follow up on the clinical follow-up or outcome of the study participant.

If the participant has access to the COVID-19 vaccine before 15 days after vaccination with the study product, the "blinding" may be performed at the participant's written request, and if the product applied was placebo, the same may be vaccinated against COVID-19 before the 15 days established by the National Immunization Program. Other details are described in the standard operating manual (MOP) of the study.

Reaction to BCG vaccine and placebo:

The BCG vaccine known to generate a local inflammatory response that lasts about 12 weeks and will be monitored throughout the study. The reactions are described below and will not be considered as adverse events:

- From the first to the second week: reddish macula lasting from 5 mm to 15 mm in diameter.
- From the third to the fourth week: pustule that forms with the softening of the center of the lesion, followed by the appearance of crust.

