- From the fourth to the fifth week: ulcer with 4 mm to 10 mm in diameter.
- From the 6th to the 12th week: scar with 4 mm to 7 mm in diameter, found in about 95% of those vaccinated.

Although the response to placebo did not cause any local vaccine reaction, which would question its use, we believe that if we did not use any intervention in the control group, bias could occur, in view of the possible reduction of precautionary measures and care in the use of personal protective equipment (PPE) in the experimental group, believing that they were "protected" by a vaccine, although its effectiveness has not been proven in this situation. On the other hand, those not vaccinated would be more careful in relation to hygiene measures and use of PPE. Using placebo, we believe that we match the usual prevention measures to COVID-19 in the study population at least in the first month of follow-up, a period prior to the onset of the lesions expected by BCG vaccination.

Adverse events:

The definition for an adverse event described in the Manual for Notification of Adverse Events and Safety Monitoring in Clinical Trials (Anvisa, 2016) will be used as a definition for an adverse event: "any adverse medical occurrence in a patient or clinical trial participant to whom a pharmaceutical product has been administered and who does not necessarily have a causal relationship to treatment. As a result, an AE can be any unfavorable and unintentional sign, symptom, or disease (including results outside the reference range), associated with the use of a product under investigation, whether related to it or not. A serious AE shall be considered to have one resulting in any adverse experience with medicinal products, biological products or devices occurring at any dose

and resulting in any of the following outcomes: a) death; b) threat to life; (c) persistent or significant disability/disability; d) requires hospitalization or prolongs hospitalization; e) congenital anomaly or birth defect; f) any suspected transmission of infectious agent by means of a drug or; g) clinically significant event."

Adverse events that do not fall within the definition of severe AE (definition above) will be graduated according to ananvisa 2016 manual:

- Light Level: Problem present less than 25% of the time, with an intensity that a person can tolerate and that rarely happened in the last 30 days;

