- Moderate Level: A problem that is present less than 50% of the time, with an intensity that interferes with the day-to-day of people and that has occurred occasionally in the last 30 days.
- Sharp Level: Problem that is present in more than 50% of the time, with an intensity that partially alters the day-to-day of the person and that has happened frequently in the last 30 days.
- Complete commitment: It means that a problem that is present in more than 95% of the time, with an intensity that completely alters the day-to-day of the person and that has occurred every day for the last 30 days.
- Unspecified: Means that there is not enough information to specify the intensity.
- Not applicable: It means that it is inappropriate to use a gradation (e.g. menstrual functions).

All EAs will be notified to the local E.R. by the study coordinator at each centre using its own form (Mop Annex 3.3). The EAs should also be reported to the coordination of the proposing institution. The EA notification form as well as proof of sending the notification to the local ZIP Code must be sent by e-mail to the coordinator of the proposing institution no later than 7 days after notification.

In the case of adverse events related to bcg vaccine (ulcer with diameter greater than 1 cm, cold subcutaneous abscess, hot subcutaneous abscess, granuloma, regional lymphadenopathy not suppurated greater than 3 cm, suppurated regional lymphadenopathy, cheloid scar or lupoid reaction), the coordinator of the proposing institution will report to the National Immunization Program of the Ministry of Health.

With regard to placebo, a minimum volume of saline solution applied intradermally will be used. The saline solution itself does not have any immunogenic component and does not cause any adverse events. It is the same solution used for intravenous or oral hydration and for dilution of medicinal products used intravenously. At intradermal application, mild pain may occur and after a few days local redness. Local signs of infection are not expected and the same vaccination standards and protocols established by the National Immunization Program will be used.

Serious adverse events:

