Adverse reactions were generally lighter and less frequently reported in the elderly (\geq 65 years of age). Analgesic and/or antipyretic medications (e.g., paracetamol-containing products) may be used to provide relief from adverse reactions after vaccination. Adverse drug reactions (ADRs) are organized by MedDRA Organ System Class (SOC). Within each SOC, the preferred terms are organized by decreasing frequency and then by decreasing severity. The frequencies of occurrence of adverse reactions are defined as: very common (\geq 1/10); (\geq 1/100 to < 1/10); unusual (\geq 1/1,000 to < 1/100); rare (\geq 1/10,000 to < 1/1,000); (1< 10,000) and unknown (cannot be estimated with available data).

Risks:

The safety of BCG revaccination among health professionals will be evaluated in order to describe possible injection site reactions and other adverse events.

In addition, we will minimize the occurrence of AS, excluding immunosuppressed individuals or using concomitant medications that impact immune responses.

Local and systemic AEs will be evaluated at relevant times through medical visits, for example in the first 20 minutes after BCG injections and in later visits, either in person or by telephone contact. The EAs will be noted and graduated according to the ANVISA Manual.

Adverse events to the BCG vaccine, more frequent have been abscess and lymphadenopathy, with higher reports for men than for women. The rates of As per 10,000 distributed doses were from 11.6 to 15.4, respectively. Unsupurated regional lymphadenopathy greater than 3 cm, supurated regional lymphadenopathy, cheloid scar, or lupoid reaction may occur. The EAs will be monitored and handled throughout the follow-up visits.

The research centers will also be open and available for extra views in case of adverse events. The manifestations will be recorded in the data collection instruments and will be treated and monitored in hospitals linked to the research centers. Similarly, the events will be notified to the National Immunization Program of the Ministry of Health, informing the batch of the vaccine applied as well as the event that occurred. Participants will receive all care and will be guaranteed assistance.

Benefits:

The results of this study may help define a form of prevention of COVID-19 for health professionals and in the future in the population as a whole.

LABORATORY PROCEDURES:

Blood collection:

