According to CNS Resolution No. 441 of 2011 (Art. 1) and Ordinance MS No. 2,201 of 2011 (Art. 3), any organized collection of human biological material collected for scientific research purposes, including samples intended for routine examinations in a clinical trial (e.g., blood count and renal function) are considered as constituents of a biorepository or biobank. The biological material will be used as provided for in the research protocol, with no further future analyses different from those foreseen. If there is a proposal for future use of the stored samples, approval in the CEP/CONEP system will be required and a new protocol and TCLE will be submitted so that each participant can choose whether or not to allow the use of the samples for future studies.

Statistical Analysis Plan:

The primary efficacy analysis will compare the cumulative incidence of SARS-CoV-2 infection and the cumulative incidence of severe forms of COVID-19.

These analyses will occur when the last enrolled research subject has completed 30 days and 6 months of preventive treatment and will be performed using the results of COVID-19 diagnostic tests, as well as the data available in participating hospitals and national electronic notification systems of COVID-19. A modified treatment intention analysis (MITT) and protocol (PP) will be performed. The safety and tolerability analysis will consist of all patients who have been randomized and received a dose of the vaccine or placebo. Based on serum immune response concentrations, we will calculate certain immunoinflammatory variables related to the use of BCG versus placebo among subjects infected and not infected by COVID-19 among the categories with COVID-19 vaccine (Coronavac® or Covishield®) and without covid-19 vaccine.

The intervention and control groups will be compared at the time of inclusion in the study in relation to sociodemographic, clinical, radiological and biochemical imaging variables, in order to evaluate the adequacy of the randomization process. Multivariate

analyses using logistic regression or Poisson models with robust variance will be used to evaluate the effect of BCG vaccine on primary and secondary outcomes. Associations will be expressed in the form of risk ratios and respective 95% confidence intervals. Data imputation may be required and the *random forest system* will be used. Statistical software R, version 10.0.

Sample size:

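### Expected BCG lesions are excluded from adverse events, the status of redness after saline is undefined, and no by-arm table of local reactions is specified, so an adverse-event comparison hides most of BCG's local excess

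*Combined protocol and SAP*

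**What the plan says.** Under Reaction to BCG vaccine and placebo, the protocol describes the local course after BCG over about 12 weeks and says it will be monitored. It then states: "The reactions are described below and will not be considered as adverse events". The list runs by week:

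- "From the first to the second week: reddish macula lasting from 5 mm to 15 mm in diameter"
- a pustule with crust in weeks 3 to 4
- "From the fourth to the fifth week: ulcer with 4 mm to 10 mm in diameter"
- for weeks 6 to 12, a "scar with 4 mm to 7 mm in diameter, found in about 95% of those vaccinated"

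The Adverse events section adopts a general definition that takes in unfavourable, unintended signs and symptoms irrespective of causal relation. It keeps larger or abnormal BCG lesions as adverse events: ulcer over 1 cm, abscess, granuloma, lymphadenopathy, keloid and lupoid reaction. On placebo, the same section says both "The saline solution itself does not have any immunogenic component and does not cause any adverse events" and "At intradermal application, mild pain may occur and after a few days local redness".

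The Risks section states the aim: "The safety of BCG revaccination among health professionals will be evaluated in order to describe possible injection site reactions and other adverse events". The Statistical Analysis Plan defines the population: "The safety and tolerability analysis will consist of all patients who have been randomized and received a dose of the vaccine or placebo". Safety of BCG in adults is secondary objective 4.

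**The concern.** The exemption takes the commonest visible effect of BCG, including an open ulcer of up to 10 mm, out of the adverse event count. Yet the general definition would otherwise reach such signs, and the Risks section groups injection-site reactions with adverse events. For saline, the plan expects redness, grants no exemption, and says that saline causes no adverse events. A data manager could not tell from this text whether a red mark after saline is to be counted.

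Nothing elsewhere in the analysis plan makes up for this. It names a safety population and offers risk-ratio models for secondary outcomes, but defines no local-reaction variable and no table by arm. Grading under Risks and the two-weekly review under Plan for monitoring and analysis of adverse events both work on adverse events, so exempted lesions do not enter them by definition.

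At stake is the tolerability picture for healthy health workers offered BCG. A report built on adverse event tables could show little or no local excess for a product that, on the plan's own account, marks nearly everyone who receives it.

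**Working it through.** The plan states no figure for this comparison, so there is nothing to reproduce. The check asks how much of BCG's local effect remains visible under each way of counting.

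**Inputs from the protocol**
- Arm size 376 (Sample size).
- Scar in about 95% of those vaccinated (Reaction to BCG vaccine and placebo). A scar is itself on the exempted list.
- BCG adverse event rates of 11.6 to 15.4 per 10,000 doses (Risks).

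**Assumed, because the documents give no rates**
- Redness after saline in 2% to 20%.
- Injection pain in 5% to 30%, equal in both arms and independent of other reactions.

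**Step 1: what the exemption removes and what it leaves**
- Removed: 0.95 × 376 = 357.2, about 357 BCG recipients.
- Left, apart from pain: 376 × 0.00116 = 0.44 to 376 × 0.00154 = 0.58 events.

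**Step 2: proportion with any counted local event**

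For two independent components a and b, the proportion with either is a + b − ab. Three readings are compared:
- A: every local reaction counted in both arms.
- B: BCG lesions exempt, saline redness counted, pain counted in both arms.
- C: saline redness also not counted, because it fits the listed appearance and week or because saline is held to cause no adverse events; pain counted in both arms.

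Worked case, redness 10% and pain 10%:
- A: BCG 0.95 + 0.10 − 0.095 = 0.955 (359 people); saline 0.10 + 0.10 − 0.01 = 0.19 (71 people); risk ratio 0.955 / 0.19 = 5.03.
- B: BCG 0.00154 + 0.10 − 0.000154 = 0.1014 (38 people); saline 0.19 (71 people); risk ratio 0.53.
- C: BCG 0.1014; saline 0.10; risk ratio 1.014.

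Over the whole assumed range:

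| Reading | Risk ratio, BCG to saline | Risk difference, percentage points |
|---|---|---|
| A, same full count | 2.2 to 13.8 | +53 to +88 |
| B, saline redness counted, BCG lesions not | 0.21 to 0.96 | −1.3 to −18.9 |
| C, neither counted | 1.00 to 1.03 | about +0.1 |

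For C, the difference is 0.00154 × (1 − pain), which is 0.0011 to 0.0015.

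**Step 3: redness alone, conditional on reading B**

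If saline redness is 5% to 20%, then 0.05 × 376 = 19 to 0.20 × 376 = 75 placebo recipients are counted. The contrast in lesions is 95 − 20 = +75 to 95 − 5 = +90 points. The contrast counted from redness alone would be −5 to −20 points. This last figure is only the assumed saline rate with its sign changed. It shows what reading B would do; it is not a prediction.

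**The case against.** A reader might infer more than the text supports, in three ways.

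- **That the plan applies opposite rules by arm and so makes BCG look safer than saline.** The placebo paragraph says saline causes no adverse events, so its redness may well not be counted. The exemption also stands under a heading naming both products and is written by appearance, size and week. The lead sentence speaks of BCG, so the wording is ambiguous, but a reversal is one reading and not the stated rule.
- **That blinded staff must guess the arm to apply the exemption.** They need not: size and week can be applied without knowing the allocation, and early redness fitting the list would tend to be handled alike in both arms.
- **That saline pain is treated more harshly.** Pain is exempted in neither arm.

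It is also fair to say that the lesions are not ignored. They are to be monitored, and injection-site photos are requested at remote contacts without distinction by arm (Study visits). Abnormal reactions remain adverse events, and the Interim Analysis Plan uses serious adverse events only, so it is essentially untouched. The safety and tolerability analysis is not expressly limited to adverse event counts. The operating manual and case report forms were not available, so a common local-reaction form may already exist.

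All of this stands, and it limits the point to what adverse event tables will show. It does not remove the point. Even on the most even-handed version of the exemption (reading C), BCG's excess all but disappears, and the plan specifies no other table in which it would appear.

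**Conclusion.** The concern holds in this form: the exemption keeps about 357 of 376 BCG recipients' expected lesions out of the adverse event count, the status of saline redness is undefined, and no by-arm tabulation of local reactions is specified. An adverse-event-based comparison for secondary objective 4 would therefore understate BCG's local reactions under either reading of the exemption.

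The count of 357 rests on the plan's 95% scar figure. The plan does not say that this figure comes from revaccinated adults, although revaccination is the question posed under Risks. The risk ratios rest in addition on assumed saline and pain rates. That the excess is hidden does not depend on those rates. A reversal in BCG's favour does depend on them, and also on saline redness being counted while BCG redness is not, so it should be reported only as a possibility.

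This should be corrected before the safety analysis. It does not affect the efficacy analyses.

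**What to change.** Reconcile Reaction to BCG vaccine and placebo, Adverse events, Risks and Statistical Analysis Plan on whether expected local reactions are adverse events, and state the status of redness after saline. Then:

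1. Record every injection-site finding (type, size, week) on one form under one rule in both arms, without reference to allocation, using the photos and contacts already planned.
2. Tabulate these by arm as solicited local reactions, with the risk difference and 95% confidence interval, separately from adverse events.
3. If an exemption is kept for notification, define it by lesion type, size and week for both arms.
4. Show the proportion with adverse events both with and without the exempted reactions.

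The cost is wording in the analysis plan and case report form and some extra data entry. The local tolerability figure for BCG will look less favourable. Notification and clinical care need not change.

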Adverse reactions observed from the phase III clinical study in the Elderly (over 60 years) up to 7 days after the administration of the second dose of the vaccine:

- Very common reaction (> 1/10): Location: pain
- Common reaction (> 1/100 and ≤ 1/10): Systemic: nausea, diarrhea, headache, fatigue, myalgia, cough, arthralgia, itching, rinorrhoea, odinofagia, nasal congestion; and Location: itching, erythema, local edema, duration
- Unusual reaction (> 1/1000 and ≤ 1/100): Systemic: vomiting, chills, decreased appetite, allergic reaction, asthena, dizziness, ecchymosis, hypothermia, discomfort in the limbs; and Location: hematoma

In addition, there are theoretical risks that vaccinated individuals could develop a more serious disease, but so far there is no report that this has happened to the virus that causes COVID-19. This vaccine was previously tested in animals and they did not present this form of infection more severe.

Adverse events related to Covishield Vaccine®:

The overall safety of the Covishield® vaccine (recombinant) is based on the interim analysis of grouped data from four clinical studies conducted in the UK, Brazil and South Africa. At the time of analysis, 23,745 \geq 18 years had been randomized and received the vaccine or control. Of these, 12,021 received at least one dose of the recombinant vaccine. Demographic characteristics were generally similar among individuals who received the vaccine and those who received control. Overall, among the individuals who received the recombinant vaccine, 90.3% were between 18 and 64 years old and 9.7% were older than 65 years or more. Most individuals were white (75.5%), 10.1% were black and 3.5% Asian; 55.8% were women and 44.2% were men. The most frequently reported adverse reactions were injection site sensitivity (> 60%); injection site pain, headache, fatigue (> 50%); myalgia, malaise (> 40%); pyrexia, chills (> 30%); and arthralgia, nausea (> 20%). Most adverse reactions were mild to moderate in intensity and usually resolved within a few days after vaccination. Compared to the first dose, adverse reactions reported after the second dose were lighter and less frequently reported.

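### The severity scale for non-serious adverse events joins duration, intensity and 30-day frequency, so short disabling reactions and harmless persistent lesions have no fitting grade

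*Combined protocol and SAP*

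**What the plan says.** The Adverse events section of the combined protocol and SAP attributes the scale to a regulator's manual and confines it to non-serious events: "Adverse events that do not fall within the definition of severe AE (definition above) will be graduated according to ananvisa 2016 manual". Four levels follow:

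- Light: "Problem present less than 25% of the time, with an intensity that a person can tolerate", and rare over the previous 30 days.
- Moderate: "A problem that is present less than 50% of the time, with an intensity that interferes with the day-to-day of people", and occasional over the previous 30 days.
- The third level: "Sharp Level: Problem that is present in more than 50% of the time, with an intensity that partially alters the day-to-day of the person", and frequent over the previous 30 days.
- The top level: "Complete commitment: It means that a problem that is present in more than 95% of the time", with daily life completely altered and the problem occurring on each of the previous 30 days.

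Two further categories cover too little information (Unspecified) and problems for which grading is inappropriate (Not applicable).

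The Risks section has local and systemic events assessed from the first 20 minutes after injection and at later visits or telephone contacts, on the same scale: "The EAs will be noted and graduated according to the ANVISA Manual".

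The section on reactions to BCG and placebo takes the expected course out of adverse events altogether: the macula, the pustule, the 4 to 10 mm ulcer and the 4 to 7 mm scar. Other lesions do count as BCG-related adverse events, among them an ulcer over 1 cm, a granuloma and a keloid scar.

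**The concern.** All conditions within a level have to hold together, and no level rests on intensity alone. That suits a chronic complaint reviewed once a month. Here the intervention is a single intradermal dose, and a reaction can be intense and brief. The same holds for other events, since adverse events count whether or not they are related to the study product. The protocol says, for example, that reactions to one of the COVID-19 vaccines participants may also receive "usually resolved within a few days after vaccination". That is not evidence about BCG, but it shows the kind of event the form will have to record.

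Safety of BCG in adults is secondary objective 4. The monitoring committee reviews adverse events every two weeks and has no formal safety stopping rule, so it relies on judgement. A scale that cannot place short, disabling events gives that judgement a poorer description of the non-serious events.

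**Working it through.** The plan states no figure on this point, so there is none to reproduce. The check converts the scale's percentages into days and tests example events against each level.

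**Inputs.** The thresholds of 25%, 50%, 50% and 95%, the intensity descriptions and the frequency clauses come from the Adverse events section. The phrase about share of time names no denominator. Step 1 assumes it is the 30-day window of the frequency clause; step 3 drops that assumption.

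**Step 1. Thresholds in days (threshold × 30).**

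- Light: 0.25 × 30 = 7.5, so under 7.5 days.
- Moderate: 0.50 × 30 = 15, so under 15 days.
- Sharp: 0.50 × 30 = 15, so over 15 days.
- Complete: 0.95 × 30 = 28.5, so over 28.5 days; the daily-occurrence clause raises this to 30.

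**Step 2. Durations as a share (days / 30).** These durations are illustrative.

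| Days present | Share | Over 50% (Sharp) | Over 95% (Complete) |
|---|---|---|---|
| 1 | 3.3% | no | no |
| 3 | 10.0% | no | no |
| 7 | 23.3% | no | no |
| 14 | 46.7% | no | no |
| 15 | 50.0% | no | no |
| 16 | 53.3% | yes | no |
| 29 | 96.7% | yes | yes |

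An event of 15 days or less fails the time condition of both upper levels at any intensity. Timing of assessment adds to this. A reaction unbroken since injection covers at most 7/30 = 23.3% at the first weekly contact and 10/30 = 33.3% at the day-10 visit. It first passes 50% on day 16.

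**Step 3. The other denominator.** If the percentage is the share of the episode, a continuous 3-day reaction is present 100% of the time and meets both upper time conditions. Complete is still out of reach, because 3 days are not each of the last 30. Sharp is doubtful, because one 3-day episode is hard to call frequent over 30 days. The result for Complete therefore does not depend on the denominator; the result for Sharp does.

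**Step 4. Two events against all four levels, on the 30-day reading.**

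| Event | Light | Moderate | Sharp | Complete |
|---|---|---|---|---|
| 3 days, completely alters daily life | time met, intensity fails | time met, intensity met only on a loose reading | time fails | time and daily occurrence fail |
| Keloid scar, always present, no effect on daily life | time fails | time and intensity fail | time met, intensity fails | time met, intensity fails |

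The first event fits no level, or is put in Moderate because anything that completely alters the day also interferes with it. The second fits no level. Neither lacks information, and the protocol gives no reason to treat either as unsuitable for grading, so the two extra categories do not resolve the conflict.

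**Step 5. Where the grades are used.** The Statistical Analysis Plan defines the safety population but no table by grade. The interim analysis uses the proportion of serious events, which are outside the scale. Reports to the national immunisation programme go by type and size of lesion. The committee's fortnightly review is not said to be by grade.

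**The case against.** The strongest reply has four parts.

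- The scale is attributed to the regulator's manual, and a trial may have to use it. That stands as a reason to keep the category on the regulator's form. It does not require the trial to summarise its own safety data the same way. The manual cannot be checked here; the point concerns the scale as this protocol writes it.
- The day counts depend on a denominator that the protocol does not give. This also stands: the 15-day and 28.5-day limits are conditional. The bar to the top level is not.
- Some short disabling events leave the scale as serious, through hospitalisation or the catch-all for clinically significant events. True, but this does not cover every short event that stops a person's normal day.
- Events are recorded on an annex to the study's operating manual, which is not available. Start and stop dates may already be on it, so that part of the fix is conditional.

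The overlap of the Light and Moderate time bands (under 25% lies inside under 50%) is a minor matter, since their intensity and frequency wording separates them.

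**Conclusion.** The point holds as a gap in the scale. A short non-serious event that completely alters daily life cannot be graded Complete on any reading. On the 30-day reading, which is an assumption, an event of 15 days or less cannot be graded Sharp either; on the episode reading Sharp is doubtful. A persistent adverse event that does not disturb daily life, such as a keloid scar, has no fitting level.

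The reach is modest: the description of non-serious events for secondary objective 4, and whatever graded data the committee receives. Serious events are unaffected.

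A reader might infer four stronger things that the documents do not support:

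- That intense short reactions will be reported as light or moderate. The conditions are joint, so such events may equally be left without a grade.
- That a harmless mark will be graded at the top. It meets only the time condition and fails on intensity.
- That the ordinary BCG ulcer and scar are misgraded. They are not adverse events under this protocol and so are not graded.
- That the grades could change a stopping decision by rule. No decision rule uses them.

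**What to change.** For the trial's safety summaries and committee reports, grade each non-serious event by its worst intensity only, using the four descriptions already in the scale: tolerable, interferes with daily life, partially alters it, completely alters it. Record start and stop dates as separate fields if the form does not already do so, so that duration is reported in its own right. Keep the combined category only where the regulator's form requires it.

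The cost is about one form field and a sentence in the Adverse events section. The downside is that staff may have to complete two severity fields for each event. The two middle descriptions also lie close together, so a line of guidance on telling them apart would help the three centres grade alike.
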